- **Number completing testing:** Number of eligible patients with a valid Xpert result plus number of eligible patients with a valid smear result entered into the NTLP Presumptive TB register, NTLP Laboratory register, GeneXpert laboratory requisition forms or NTLP treatment register, or with a test result recorded in the GeneXpert machine data. Testing must be completed within six months of enrolment. If the test result is missing and cannot be found in the GeneXpert machine data, it will be assumed that the patient was tested within six months of enrolment. Definitions of valid results are as follows:
 - A positive Xpert (Ultra) result with a semi-quantitative result of high, medium, low, or very low for all eligible patients; a positive Xpert Ultra result with a semi-quantitative result of trace for eligible HIV-positive patients; or a second positive Xpert Ultra result (including trace) if the initial result is trace-positive for eligible HIV-negative patients;⁶

- A negative Xpert result for all eligible patients;
- One positive OR two negative smear results for eligible HIV-negative/HIV status unknown patients.

- **Microbiologically-confirmed TB:** A positive smear and/or positive Xpert test result (as defined above) entered into the NTLP Presumptive TB register, NTLP Laboratory register, GeneXpert laboratory requisition forms, NTLP treatment register, and/or GeneXpert machine data (intervention sites only) within six months of enrolment. **Number diagnosed:** Number of eligible patients with microbiologically-confirmed TB via a positive smear and/or valid Xpert test result entered into the NTLP Presumptive TB register, NTLP Laboratory register, GeneXpert laboratory requisition form, NTLP treatment register, and/or GeneXpert machine data within six months of enrolment.
- **Number with RIF resistance detected by Xpert:** Number of eligible patients with RIF resistance identified by Xpert testing entered into the GeneXpert laboratory requisition forms and/or NTLP Laboratory registers within six months of enrolment .
- **Number with RIF resistance confirmed by culture:** Number of eligible patients with: (1) RIF resistance detected by Xpert testing entered into the GeneXpert laboratory requisition forms and/or NTLP Laboratory registers, and (2) RIF resistance confirmed by culture-based DST or a second molecular assay as determined by review of Lab Register at MDR treatment center within six months of enrolment .

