Number with RIF resistance detected by Xpert/number with RIF resistance confirmed by culture*	Number with RIF resistance detected by Xpert/number with RIF resistance confirmed by culture	None
Proportion with RIF resistance detected by Xpert/proportion with RIF resistance confirmed by culture*	Number with RIF resistance detected by Xpert/number with RIF resistance confirmed by culture	Number enrolled
Time to microbiologically-confirmed TB**	Time-to-diagnosis if microbiologically-confirmed TB	None
C. Treatment		
Outcome	Numerator	Denominator
Number treated for TB*	Number treated	None
Proportion treated for TB*	Number treated	Number enrolled
Number treated for microbiologically-confirmed TB*	Number diagnosed AND treated	None
Proportion treated for microbiologically-confirmed TB*	Number diagnosed AND treated	Number enrolled
Proportion with microbiologically-confirmed TB treated*	Number diagnosed AND treated	Number diagnosed
Time-to-treatment of microbiologically-confirmed TB	Time-to-treatment if microbiologically-confirmed TB and treated	None
D. Follow-up		
Outcome	Numerator	Denominator
Number with microbiologically-confirmed TB completing treatment	Number diagnosed AND completing treatment	None
Proportion with microbiologically-confirmed TB completing treatment	Number diagnosed AND completing treatment	Number diagnosed AND treated
Number who died within 6 months	Number died	None

Proportion who died within 6 months***	Number died	Number enrolled
Number who died within 6 months	Number diagnosed AND died	None
Proportion who died within 6 months***	Number diagnosed AND died	Number diagnosed
Number who died within 6 months	Number treated AND died	None
Proportion who died within 6 months***	Number treated AND died	Number treated

*Outcome will be assessed within 1 day and within 14 days of enrolment. One day was chosen because the intervention focuses on same-day diagnosis and treatment. 14 days was chosen because the diagnostic process could take 7-10 days in the control arm depending on the frequency of sample transport to Xpert testing sites.

**For the control arm, missing Xpert result dates will be recorded as the next scheduled date of sputum transportation from the health center to the GeneXpert facility (results from the previous batch of testing are returned when the next batch of samples are picked up). For the intervention arm, missing Xpert result dates will be recorded as the day following sample collection.

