B. Diagnosis							
Number diagnosed with microbiologically-confirmed TB (by day 1)	# GM						
Number diagnosed with microbiologically-confirmed TB (by day 14)	# GM						
Proportion diagnosed with microbiologically-confirmed TB (by day 1)	% (n/N) GM %						
Proportion diagnosed with microbiologically-confirmed TB (by day 14)	% (n/N) GM %						

Number with RIF resistance detected by Xpert/ number with RIF resistance confirmed by culture (by day 1)	# GM						
Number with RIF resistance detected by Xpert/ number with RIF resistance confirmed by culture (by day 14)	# GM						
Proportion with RIF resistance detected by Xpert/proportion with RIF resistance confirmed by culture (by day 1)	% (n/N) GM %						
Proportion with RIF resistance detected by Xpert/proportion with RIF resistance confirmed by culture (by day 14)	% (n/N) GM %						
Time to microbiologically-confirmed TB	# GM						
C. Treatment							
Number treated for TB (by day 1)	# GM						
Number treated for TB (by day 14)	# GM						
Proportion treated for TB (by day 1)	% (n/N) GM %						
Proportion treated for TB (by day 14)	% (n/N) GM %						
Number treated for microbiologically-confirmed TB (by day 1)	# GM						
Number treated for microbiologically-confirmed TB (by day 14)	# GM						
Proportion treated for microbiologically-confirmed TB (by day 1)	% (n/N) GM %						
Proportion treated for microbiologically-confirmed TB (by day 14)	% (n/N) GM %						
Proportion with microbiologically-confirmed TB treated (by day 1)	% (n/N) GM %						
Proportion with microbiologically-confirmed TB treated (by day 14)	% (n/N) GM %						
Time-to-treatment of microbiologically-confirmed TB	GM						
D. Follow-up							

Number with microbiologically-confirmed TB completing treatment	# GM						
Proportion with microbiologically-confirmed TB completing treatment	% (n/N) GM %						
Number who died within 6 months	# GM						
Proportion who died within 6 months	% (n/N) GM %						

GM geometric mean; GM % geometric mean of the cluster-level proportions

Table 5c: Sub-group analyses for selected secondary outcomes: stratum-specific unadjusted and adjusted risk ratios (95% confidence intervals) and associated P-values for interaction

Secondary outcomes	I:	C:	RR (95% CI)	P-value	Adjusted RR (95% CI)	P-value	P-value for interaction
A. Proportion completing testing							
HIV-positive	% (n/N)						
HIV-negative	% (n/N)						
Male	% (n/N)						
Female	% (n/N)						

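### Confirmed rifampin resistance is defined over six months but compared between arms only by day 1 and day 14, so later confirmations drop out of the formal comparison

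*Combined protocol and SAP*

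**What the plan says.** All references are to the amended SAP unless stated.

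- **Definitions (section 3.4).** The Xpert-detected outcome counts eligible patients who have "RIF resistance identified by Xpert testing entered into the GeneXpert laboratory requisition forms and/or NTLP Laboratory registers within six months of enrolment". The confirmed outcome also requires "RIF resistance confirmed by culture-based DST or a second molecular assay as determined by review of Lab Register at MDR treatment center within six months", counted from enrolment.
- **Outcome table (section 3.4, Diagnosis).** The two outcomes share one count row, "Number with RIF resistance detected by Xpert/number with RIF resistance confirmed by culture", and one proportion row. Both rows are starred, and the star reads "Outcome will be assessed within 1 day and within 14 days of enrolment". The reason given for the later time is that "14 days was chosen because the diagnostic process could take 7-10 days in the control arm", depending on how often samples travel to the testing site.
- **Annex Table 5b.** The RIF rows are given by day 1 and by day 14. There is no six-month row.
- **Who is counted (section 3.4, eligible patient).** Patients found RIF-resistant by Xpert contribute to no primary or secondary analysis other than the RIF outcomes.
- **Sources (section 3.4).** GeneXpert machine data are listed for the number diagnosed. For RIF resistance only requisition forms and laboratory registers are listed.

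The two protocols and SAP version 1.0 have the same six-month definitions with day-1 and day-14 assessment.

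**The concern.** Confirmation is a later step than detection. It needs an Xpert result, contact with an MDR centre, and then a second test recorded in that centre's laboratory register. The 14-day limit is explained only by the time the control diagnostic process may take. A patient confirmed after day 14 but within six months meets the definition, yet neither Table 5b row counts that patient as confirmed. The amended protocol (Patient-level data collection) has staff call MDR centres about additional testing, so the plan gathers information that it does not then compare.

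Two drafting points add to this. A resistant result present only in the device would, read literally, remove the patient from every other outcome without adding to the RIF count. And the label says confirmed by culture, although a second molecular assay also qualifies.

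At stake is the one group of outcomes for which RIF-resistant patients are kept in the analysis.

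**Working it through.** The documents give no event rate, power or turnaround for the RIF outcomes, so there is no planned figure to reproduce. The check is a comparison of texts, followed by an illustration of size.

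**1. Texts side by side**

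| Element | Xpert-detected | Confirmed |
|---|---|---|
| Window in definition | six months | six months |
| Outcome row | shared, starred | shared, starred |
| Rows in Annex Table 5b | day 1, day 14 | day 1, day 14 |
| Six-month row | none | none |
| Rule for the event date | time-to-diagnosis covers Xpert results | none stated |

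The last line matters: without a confirmation date, a day-14 cut cannot be applied consistently.

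**2. Time left for confirmation inside 14 days**

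- Control, if the process takes 7 days: 14 - 7 = 7 days.
- Control, if it takes 10 days: 14 - 10 = 4 days.
- Intervention, with a same-day onsite result: 14 - 0 = 14 days.

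The shortfall can therefore differ by arm, whatever the confirmatory test takes.

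**3. Illustrative number of cases**

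Inputs:
- N = 5,360 (SAP section 3.5, which equals 20 x 268) or 11,283 (amended protocol, Overview).
- Share with confirmed TB = 6.7%. This is the baseline share starting treatment within two weeks (section 3.5), used only as a stand-in. The planning example in the same section has 95 and 40 diagnosed per 1,000, which averages (95 + 40)/2 = 67.5 per 1,000, about the same.
- r = RIF-resistant share among these, assumed 1-5%.
- f = share of resistant cases confirmed by day 14, assumed 5-50%.

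Expected confirmed cases E = N x 0.067 x r x f, and the Poisson chance of none is exp(-E).

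If every case were confirmed within six months (f = 1):
- lowest: 5,360 x 0.067 x 0.01 = 3.6
- middle: 11,283 x 0.067 x 0.03 = 22.7
- highest: 11,283 x 0.067 x 0.05 = 37.8

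By day 14, both arms together:

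| f | Middle case: E | P(none) | Lowest case: E | P(none) |
|---|---|---|---|---|
| 5% | 1.1 | 0.32 | 0.18 | 0.84 |
| 10% | 2.3 | 0.10 | 0.36 | 0.70 |
| 25% | 5.7 | 0.003 | 0.90 | 0.41 |
| 50% | 11.3 | <0.001 | 1.8 | 0.17 |

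Zero is possible but does not follow from the documents.

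**4. Spread over 20 clinics, six-month window**

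With equal clinics, the middle case gives 22.7/20 = 1.13 per clinic. The chance of a zero clinic is exp(-1.13) = 0.32, so about 20 x 0.32 = 6 clinics have none. The lowest case gives 3.6/20 = 0.18, exp(-0.18) = 0.84, about 17 clinics. The highest gives 37.8/20 = 1.89, exp(-1.89) = 0.15, about 3 clinics. The six-month comparison is better, but still imprecise.

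**5. What the zero rule does**

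For proportions (section 4.4.4.2), 0.5 event is added to every cluster if any cluster has none. If all clusters were zero, each risk would be 0.5 divided by cluster size, and the risk ratio would be the inverse ratio of geometric mean cluster sizes. With intervention clusters 1.5 times larger (assumed), that is 1/1.5 = 0.67, an artefact and not an effect. This bears only on the all-zero case, which a short window makes more likely.

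**The case against.** **Six months may be only an outer limit.** The number diagnosed is built the same way: defined within six months, then starred. That reading is possible. But patients diagnosed after day 14 still contribute to time to diagnosis, treatment completion and death among those diagnosed. Confirmed RIF resistance has no such further outcome.

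**The information is not lost.** Annex Table 3 shows RIF result and DST-confirmed MDR status by arm, with no day-1 or day-14 limit. This stands and narrows the point: what is missing is a formal comparison. Table 3 does not supply one. It is descriptive, its confirmed category names only DST, and section 4.4.2 describes it as covering the 12 months after 22 October 2018.

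**Stronger readings that a reader might infer.** One is that the confirmed rows will be empty and no comparison can be made. The documents do not support this. They give no confirmation turnaround, a second molecular assay counts, and Xpert-detected resistance in the same row can be compared at day 14. Another is that day-1 detection in control is near zero by design. The footnote says only that the process could take 7-10 days. HIV-infected control patients give sputum for Xpert at the first visit, and a day-1 contrast is what the intervention aims for.

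**The device-only result is hypothetical.** Intervention laboratory staff are trained in recording results, and records are reconciled across sources. No frequency is given, so this is a wording gap of unknown size.

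**Few events in any case.** This also stands. A longer window recovers cases but does not make the ratio precise.

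**Conclusion.** The point holds in a limited form. The six-month definition of confirmed RIF resistance does not match its assessment at day 1 and day 14, and confirmations after day 14 enter no planned between-arm comparison. The time available for confirmation can differ by arm: 4-7 days in control if the process takes 7-10 days, against up to 14 after a same-day onsite result. Day-14 confirmed counts are likely to be sparse, but how sparse depends on a turnaround and a resistance share that the documents do not give. With an assumed 1-5% resistant among 6.7% of patients, the whole trial would yield about 4 to 38 cases. The source omission and the label are drafting errors to correct at the same time.

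These are secondary outcomes. RIF-resistant patients are excluded from the primary analysis, so the primary result does not change. The amendment is still worth making, because it lets the plan report what it defines.

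**What to change.** In SAP section 3.4 and Annex Table 5b:

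1. Split the combined row into Xpert-detected and confirmed resistance, for the count and for the proportion.
2. Keep day 1 and day 14 for Xpert-detected resistance, and add its six-month count.
3. Report confirmed resistance within six months of enrolment, and state that the date used is the confirmation date in the MDR-centre record.
4. Add GeneXpert machine data, for both arms, to the sources for the RIF definitions.
5. Rename the second outcome as confirmed by culture-based DST or second molecular assay.

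The cost is wording in the SAP and its tables, using data already collected. MDR-centre follow-up is already planned, and hub machine data are already to be sought for missing control-arm dates. Day-1 and day-14 Xpert detection is kept; only the day-1 and day-14 confirmed rows are replaced. Counts will remain small, so the six-month comparison should be presented as imprecise.

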- **Number diagnosed:** Number of eligible patients with microbiologically-confirmed TB via a positive smear and/or valid Xpert test result entered into the NTLP Presumptive TB register, NTLP Laboratory register, GeneXpert laboratory requisition forms, NTLP treatment register, and/or GxAlert database within 6 months of *date enrolled*.
- **Number with suspected RIF resistant TB:** Number of eligible patients with RIF resistance identified by Xpert testing entered into the GxAlert database, GeneXpert laboratory requisition forms, and/or NTLP Laboratory registers within 6 months of *date enrolled*.
- **Number with confirmed RIF resistant TB:** Number of eligible patients with RIF resistance identified by Xpert testing entered into the GxAlert database, GeneXpert laboratory requisition forms, and/or NTLP Laboratory registers, and RIF resistance confirmed by culture-based DST or a second molecular assay as determined by review of Lab Register at MDR treatment center within 6 months of *date enrolled*.
- **Number treated:** Number of eligible patients entered into the NTLP Treatment register as having started Category I or II regimen, or started on MDR treatment at the MDR treatment center as determined by review of Treatment Register at MDR treatment center within 6 months of *date enrolled*.
- **Number completing treatment:** *Number treated* and with a treatment outcome of cured or completed entered into the NTLP Treatment register or indicated by MDR treatment center staff through direct follow up.
- **Number died:** *Number treated* and with a treatment outcome of died entered into the NTLP Treatment register within 6 months of *date enrolled*, or number eligible with treatment outcome entered as died on direct follow-up form.
- **Time-to-diagnosis:** Number of days from *date enrolled* to earliest date of positive smear or valid Xpert result recorded in NTLP Presumptive TB register, NTLP Laboratory register, GeneXpert laboratory requisition form, NTLP treatment register, or GxAlert database within 6 months of *date enrolled*.
- **Time-to-treatment:** Number of days from *date enrolled* to treatment start date entered into NTLP Treatment register if treatment start date is within 6 months of *date enrolled*.

Primary Outcome

Outcome	Numerator	Denominator
Number treated for microbiologically-confirmed TB within 14 days of referral for sputum-based testing	Number diagnosed and time-to-treatment within 14 days	None

Secondary Outcomes

A. Testing		

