3.4 Outcomes

Definitions used to assess study outcomes

- **Eligible patient:** clinic attendees satisfying our inclusion and exclusion criteria (as listed above) AND excluding patients aged <18 years or those with a documented prior history of TB treatment (e.g., reason for Xpert testing or TB treatment marked as treatment failure, relapse, treatment after loss to follow-up, etc.). In addition, patients identified as RIF resistant by Xpert testing will not contribute to the primary and secondary analysis except for the number and proportion with RIF resistance detected by Xpert or RIF resistance confirmed by culture.
- **Number enrolled (i.e., number evaluated for TB):** Number of eligible patients identified over a defined enrolment period through review of the NTLP Presumptive TB register, NTLP Laboratory register, GeneXpert laboratory requisition forms and NTLP Treatment register at each study site (includes patients treated for TB without undergoing any sputum testing).
- **Date enrolled:** Earliest date recorded in the NTLP Presumptive TB register, NTLP Laboratory register, GeneXpert laboratory requisition form, NTLP Treatment register or machine data. Records will be prospectively reviewed using name, sex, and age to identify patients presenting multiple times over the study period. Visits occurring within six months of enrollment will be considered as part of the same episode.
- **Number referred for testing:** Number of eligible patients identified through review of the NTLP Presumptive TB register, NTLP Laboratory register and GeneXpert laboratory requisition forms at each study site. Patients indicated as new in the NTLP Treatment Register will also be considered testing referrals.
- **Number tested:** Number of eligible patients with any smear or Xpert result entered into the NTLP Presumptive TB register, NTLP Laboratory register, GeneXpert laboratory requisition forms, or NTLP treatment register at each study site, or with a test result recorded in the onsite GeneXpert machine. Results must be dated within six months of enrolment. If result date is missing and cannot be found in the GeneXpert machine data, it will be assumed that the patient was tested within six months of enrolment.

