- **Number treated:** Number of eligible patients entered into the NTLP Treatment register as having started Category I or II regimen.
- **Number completing treatment:** Number treated and with a treatment outcome of cured or completed entered into the NTLP Treatment register.
- **Number died, among those initiated on TB treatment:** Number treated and with a treatment outcome of died entered into the NTLP Treatment register within six months of enrolment , or number treated and confirmed dead by next of kin with a date of death within six months of enrolment.
- **Number died, among those with confirmed TB:** Number diagnosed and with a treatment outcome of died entered into the NTLP Treatment Register within six months of enrolment, or number diagnosed and confirmed dead by next of kin with a date of death within six months of enrolment.
- **Number died, among all those eligible:** Number treated and with a treatment outcome of died entered into the NTLP Treatment register within six months of enrolment, or number traced with a death recorded
- **Time-to-diagnosis:** Number of days from *date enrolled* to earliest date of positive smear or valid Xpert result recorded in NTLP Presumptive TB register, NTLP Laboratory register, GeneXpert laboratory requisition form, or NTLP treatment register within six months of enrolment . For the control arm, attempts will be made to abstract the missing Xpert result dates from machine data from GeneXpert machines at testing hubs. For patients with microbiologically confirmed TB who are missing the smear or Xpert result date, the date of treatment initiation will be used as the date of diagnosis.
- **Time-to-treatment:** Number of days from *date enrolled* to treatment start date entered into NTLP Treatment register if treatment start date is within six months of enrolment.

Primary Outcome

Outcome	Numerator	Denominator
Number treated for microbiologically-confirmed TB within 14 days of date enrolled.	Number diagnosed and time-to-treatment within 14 days	None

Secondary Outcomes

A. Testing		
Outcome	Numerator	Denominator
Number referred for TB testing	Number referred for testing	None
Proportion completing testing	Number completing testing	Number enrolled
B. Diagnosis		
Outcome	Numerator	Denominator
Number diagnosed with microbiologically-confirmed TB*	Number diagnosed	None
Proportion diagnosed with microbiologically-confirmed TB*	Number diagnosed	Number enrolled

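### Two unranked rules, one of them set by trial arm, date a missing Xpert result, so time to diagnosis can depend on the arm or on the analyst

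*Combined protocol and SAP*

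**What the plan says.** All of the following is in section 3.4 of the current SAP unless stated.

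- **Footnote **, attached to time to microbiologically-confirmed TB.** In control, "missing Xpert result dates will be recorded as the next scheduled date of sputum transportation from the health center to the GeneXpert facility", with the explanation in brackets that "results from the previous batch of testing are returned when the next batch of samples are picked up". For the other arm: "For the intervention arm, missing Xpert result dates will be recorded as the day following sample collection".
- **Time-to-diagnosis definition.** The clock runs from date enrolled "to earliest date of positive smear or valid Xpert result recorded in NTLP Presumptive TB register" or another listed register or form. For confirmed patients "who are missing the smear or Xpert result date, the date of treatment initiation will be used as the date of diagnosis". This applies to both arms.
- **Recovery of dates.** The same definition says "For the control arm, attempts will be made to abstract the missing Xpert result dates from machine data from GeneXpert machines at testing hubs". It names no such step for the intervention arm and does not list onsite machine data as a source. Under Number tested, however, the SAP does look there: "If result date is missing and cannot be found in the GeneXpert machine data, it will be assumed that the patient was tested" inside the six-month window. The protocol's process metrics (Implementation Outcomes) also take intervention result dates from the GeneXpert software.
- **How the overlap arose.** In SAP version 1.0 the Time-to-diagnosis definition ended with its sources ("GeneXpert laboratory requisition form, NTLP treatment register, or GxAlert database within 6 months of" date enrolled) and had no treatment-date rule, so the footnote stood alone. The current SAP adds the treatment-date rule and keeps the footnote for time to diagnosis. It removes the footnote mark from time-to-treatment.
- **Sensitivity analyses.** The two in section 4.4.3 concern trace-positive results only.

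**The concern.** The outcome is restricted to confirmed patients. Every treated patient whose diagnosis date rests on a missing Xpert date therefore falls under both rules, and the SAP does not say which comes first. Two analysts following the text could report different values.

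The footnote's fill is also a function of randomised arm. Speed of diagnosis is what this outcome measures, so an arm-specific fill can put a difference into the data that was not observed. The control rule itself has two readings: the first pickup after collection or, following the bracket, the later pickup that brings the result back.

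At stake is one secondary outcome, plus the day-1 diagnosis rows if they use the same dates. The latter is an inference: those rows carry footnote * only, and the SAP does not say whether footnote ** reaches them.

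**Working it through.** The documents give no time-to-diagnosis figure and no missing share, so there is no stated figure to reproduce.

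**1. The rules on single patients (sampled on the enrolment day, day 0).**
- Intervention, treated on day 5: diagnosed on day 1 by the footnote, on day 5 by the definition.
- Control, sampled on Monday with a weekly Thursday pickup, treated on day 12: day 3 (next pickup), day 10 (pickup that returns the result) or day 12 (treatment date).

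**2. No true difference, footnote first.**

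Assumptions: an equal missing share m in both arms; dated times near 1 day; weekday collection on day 0; control fill at the next pickup strictly after collection. I add 0.5 day before taking logs because same-day times are 0 and the SAP states no offset. Annex Table 1 gives transport as once, or two or more times, per week.

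L = mean ln(control fill + 0.5) − ln(1.5), and GMR (intervention/control) = exp(−m × L).

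| Pickups | Mean control fill | L | m = 2% | m = 5% | m = 20% |
|---|---|---|---|---|---|
| Weekly | 4.2 days | 1.007 | 0.980 | 0.951 | 0.818 |
| Twice weekly | 2.4 days | 0.576 | 0.989 | 0.972 | 0.891 |

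For example, weekly at 20%: exp(−0.20 × 1.007) = 0.818. Offsets from 0 to 1 widen the 20% range to 0.78-0.91.

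As a check on the 2% case, take a between-cluster SD of 0.2-0.3 (borrowed from the SAP's Table 3, which concerns another outcome), 16 degrees of freedom and weekly pickup with collection on all seven days. A nominal 5% test then rejects 5.3-5.8% of the time.

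**3. Variations, still with no true difference.**
- Result-return reading, no earlier dated smear (mean fills 4.6 and 9.8 days): 0.942 and 0.909 at 5%; 0.787 and 0.683 at 20%.
- Only 30-60% of control cases resting on Xpert, the rest having an earlier dated smear: 0.99-0.89 with dated times near 1 day.
- Machine dates leaving 0-2% missing in the intervention arm against 5-20% in control, dated times of 1-3 days: 0.82-1.06.
- Treatment date first, so that the footnote reaches only the untreated (7-30% of those missing, using the pre-treatment losses in section 3.5): exp(−0.0035 × 0.576) = 0.998 to exp(−0.06 × 1.007) = 0.941 on next pickup. The result-return reading with weekly pickup and no offset gives 0.87.

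**4. A real difference.**

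Footnote * says the control process could take 7-10 days. Assume true times of 7 days in control and 0 or 1 day in the intervention arm, with 20% missing. The true GMR is 0.5/7.5 = 0.07 or 1.5/7.5 = 0.20. With weekly next-pickup fills, the geometric mean of (fill + 0.5) is 1.5 × exp(1.007) = 4.11.
- Intervention time 0: (0.5^0.8 × 1.5^0.2)/(7.5^0.8 × 4.11^0.2) = 0.09.
- Intervention time 1: 1.5/(7.5^0.8 × 4.11^0.2) = 0.23.

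Both move toward 1. The weekly result-return reading with intervention times of 1 day moves slightly the other way, from 0.20 to 0.19.

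**5. Day-1 diagnosis, only if the same fills are used and collection is on the enrolment day.**

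RR = ((1−m)p + m)/((1−m)p + mq), where p is the dated share diagnosed by day 1 and q the share of control fills by day 1 (both assumed).
- p = 0.70, q = 0.4, m = 5%: 1.04.
- p = 0.30, q = 0.2, m = 20%: 1.57.

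**The case against.** The strongest reply is that the fills imitate how each arm works: results return with the transport in control and come from an onsite machine in the intervention arm. If truly missing dates resemble the fills, the rule does no harm. It may even be conservative, since next-pickup fills averaging 2.4-4.2 days are shorter than the 7-10 days in footnote *. The intervention fill of one day is also no faster than the same-day aim. This stands. Identical times in both arms are a stress test, not the expected state.

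The missing share may also be small. The protocol's Data Management section plans completeness checks on result dates, re-review of the register photographs and a call to each health center after every two-week extraction. Hub machine data and an earlier dated smear reduce the control share further. This also stands, and 5-20% is purely assumed.

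The calculation sets collection at day 0, whereas the outcome runs from enrolment. In control, patients not known to be HIV-infected give the Xpert specimen at the third visit. The day-1 figures do not describe them.

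None of this supplies the missing order of rules, or a planned analysis that would show whether the fills matter.

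A reader might infer that the footnote favours the intervention. The documents do not support a fixed direction, as steps 3 and 4 show.

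**Conclusion.** The point holds as a conflict within the current SAP. Two rules date the same missing result, their order is not stated, one depends on randomised arm, and its control version has two readings. That conclusion needs no assumed figure, and the text should be fixed.

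The size does rest on assumptions. With no true difference, equal missingness, the footnote first and next pickup, the GMR is about 0.95-0.97 at 5% missing and 0.82-0.89 at 20%, and negligible near 2%. Under a real effect the fill may shrink the difference, so the direction is uncertain.

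A reader might also infer that the primary result is at risk. The date rules do not reach it: its 14-day clock, like time-to-treatment, runs from date enrolled to treatment start and uses no filled Xpert date.

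**What to change.** 1. In section 3.4, state one order for both arms: recorded result date, then machine date (onsite or hub), then a single named fallback. Remove the overlap between footnote ** and the Time-to-diagnosis definition. Say whether the order also governs the day-1 and day-14 diagnosis rows. The choice of fallback is a trade-off to be stated: a treatment date is itself affected by the intervention and, with empiric treatment, can precede testing.
2. Report missing and filled dates by arm and source. Add one sensitivity analysis of time to diagnosis and day-1 diagnosis using observed (recorded or machine) dates only.

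The cost is SAP wording, one table and one analysis. Hub dates are already to be abstracted, and onsite machine data are already a trial source. One limit to state is that a hub machine date may precede the result's return to the clinic. No further analysis of the primary outcome is needed for this point.

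One matter should be raised separately, and it is not editorial. In section 3.4, the definition of microbiologically-confirmed TB limits machine data to intervention sites, while the adjacent Number diagnosed definition does not. The SAP's Table of Amendments records use in both arms. The two definitions should be reconciled, because the case definition feeds the primary numerator.
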